4.1.2. Baseline Definition

For all endpoints (except for noted in baseline definitions) the baseline values will be derived as below.

If there is unscheduled data on the day of Week 0, the value immediately before Nucala administration will be adopted.

When to be collected	Baseline value	
At Screening	At Week 0	
X	-	Screening data
-	Х	Week 0 data
Х	Х	Week 0 data

Retrospective data

Definition

1) Observed data within 12 weeks before the first dose of Nucala for EGPA (i.e. (date of first dose of Nucala – 84 (days) \leq < date of first dose of Nucala)

- Clinical symptoms as assessed by 9 organ-systems
- Concomitant medication
- Medical/Surgical procedures
- Clinical laboratory parameters
- Lung function
- Ejection fraction

2) Observed data within 48 weeks before the first dose of Nucala for EGPA (i.e. (date of first dose of Nucala -336 (days) $\leq <$ date of first dose of Nucala)

- Hospitalization for EGPA-related events
- ER/Unscheduled visit for EGPA-related events
- Asthma exacerbations

The retrospective data will be summarized in the same manner as the observation period.

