#### **Screening period**

During the screening period (0-4 weeks), all participants are assessed to determine whether they meet the eligibility criteria. Retrospective data are collected for reference regarding the clinical symptoms/findings and laboratory parameters before the first dose of Nucala (at least 96 weeks [approximately 2 years] before). These retrospective data should be from physician source/medication record. By using the retrospective data,

information could be provided about the change from pre-Nucala exposure to the end of this study, of which a period would be approximately 4 years.

Any participant who completes assessments during the screening period but does not continue in the study beyond Baseline or is subsequently found to be ineligible for the study prior to Baseline, is classified as Screen Failure. Information collected for the participant classified as Screen Failure is detailed in the guideline for eCRF entry. Rescreening is permitted once only.

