# 4.7. Subgroup Analysis

The following subgroups are of interest in this study. A separate exploratory analysis of the prespecified endpoints within each subgroup will be carried out. Subgroup categories may be further collapsed if there are a small number of participants within a subgroup.

The following subgroups are of interest:

- Sex
- Age
- Duration of EGPA disease
- Severity of EGPA disease
- Adherence to recommended treatment regimen for Nucala
- Current medical conditions (e.g., presence/absence of asthma, allergic rhinitis, etc.)
- Medical history (e.g., presence/absence of asthma, allergic rhinitis, etc.)
- Prior use of Nucala for asthma

- Previous therapeutic regimen for EGPA disease (e.g., presence/absence of plasma exchange therapy, operation, etc.)
- Prior use of other biological medications
- ANCA
- Favourable treatment response with Nucala
- Immuno-suppressive therapy
- EGPA disease relapse
- Clinical symptoms
- COVID-19 infection

Further details of the subgroup analyses will be provided in the RAP.

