#### 9. APPENDIX

# 9.1. APPENDIX 1: SCHEDULE OF ACTIVITIES (SOA)

Procedure	Screening		Observation period			Follow-up 
Time period for which data should be collected at	Up to 4 we	eks before Week 0 	Week 0	Week 12 to 96;	Early	Up to 96 weeks
usual EGPA healthcare visits,	(Screening  )	(Retrospective data 	Baseline	no more frequently than	withdrawal	after Week 0
if this is possible		collection)		every 12 weeks (±4weeks)		
Informed consent	X 					
Inclusion and exclusion criteria	Χ					
Demography	X					
Administration status of Nucala for EGPA	X		Χ	Χ	Χ	X 5
Concomitant medication	X	X6	Χ	Χ	Χ	X
Concomitant therapies	X	X 	Χ	X	Χ	X
Adverse events	X		+			→
Clinical symptoms		Χ	Χ	Χ	Χ	X
Hospitalization for EGPA-related events		X8	Χ	X	Χ	X
ER/Unscheduled visit for EGPA-related events		X8	Χ	Χ	Х	X
Asthma exacerbation		X8	Χ	Χ	Х	X
Clinical laboratory parameters  , if performed		Х	Χ	Χ	Χ	X
Lung function, if performed		Х	Χ	X	Χ	X
Ejection fraction, if performed		Х	Χ	Χ	Χ	X
Pregnancy reporting			•		-	
EGPA recurrence						X

- 1. The follow-up period is only applicable for participant who discontinued the treatment. If drug-related adverse events occurred, contact the sponsor.
- 2. Screening and Week 0 can occur on the same day.
- 3. Retrospective data within 12 weeks (otherwise specified) before the first dose of Nucala for EGPA.
- 4. Informed consent must be obtained prior to start of any study's procedure.
- 5. Only for in case of receiving the re-treatment of Nucala.
- 6. Only for other biological products, Nucala for asthma, corticosteroid, immunosuppressants, and immunoglobulin.
- 7. Only for EGPA therapies.
- 8. Number of events within 48 weeks before the first dose of Nucala for EGPA.
- 9. Haematological parameters tested are:

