4.8. Changes to Protocol Defined Analyses

There were no changes or deviations to the originally planned statistical analysis specified in the protocol amendment 01 (Dated: 27-JUL-2020).

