6.2.2. Study Period

Assessments and events will be classified according to the time of occurrence relative to the study period.

Screening period is defined as 0-4 weeks before the date of dose of Nucala at Week 0.

Observation period is defined as time from the date of dose of Nucala at Week 0 to the stop date of Nucala +28 days for the participants who did not withdraw from study, or the first treatment discontinuation date +28 days for the participants who withdraw from study. If the date of dose of Nucala at Week 0 is missing, the latest available date between the screening visit date and the Week 0 visit date will be used for the start date of the observation period. When the last Nucala stop date is missing, the last Nucala start date will be imputed.

Follow-up period is defined as time from the first treatment discontinuation date +29 days to 96 weeks within the observation period at maximum. The follow-up period is only applicable for the participants who discontinued the treatment.

Retrospective period is defined as time (within 12 weeks) before the first dose of Nucala. For data of hospitalization for EGPA-related events and ER/Unscheduled visit for EGPA-related events the period is defined as time (within 48 weeks) before the first dose of Nucala.

The study periods to use for summaries on each endpoint are as below.

A:	PMS period	B: Observation period
Retrospective		
period		

Participants who completed the study

Participants who discontinued and moved to the follow-up period

C:	PMS period	D: Observation	E: Follow-up
Retrospective		period	period
period			

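### The retrospective reference described as pre-Nucala starts from the first dose for EGPA, so it can include time on Nucala for asthma, and no visible planned display separates those participants

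*SAP*

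**What the plan says.** SAP 4.1.2 defines two retrospective windows. Hospitalizations, emergency or unscheduled visits and asthma exacerbations use "Observed data within 48 weeks before the first dose of Nucala for EGPA". Clinical symptoms, concomitant medication, procedures, laboratory values, lung function and ejection fraction use "Observed data within 12 weeks before the first dose of Nucala for EGPA". The Protocol's Schedule of Activities has the same anchor: footnote 3 reads "Retrospective data within 12 weeks (otherwise specified) before the first dose of Nucala for EGPA", and footnote 8 sets 48 weeks for the event counts.

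Protocol 3.1 (Screening period), repeated in SAP 1.2, gives the purpose of these data: "information could be provided about the change from pre-Nucala exposure to the end of this study".

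The Protocol foresees earlier treatment. Footnote 6 of the schedule restricts retrospective medication to "Only for other biological products, Nucala for asthma, corticosteroid, immunosuppressants, and immunoglobulin". Protocol 4.7 lists "Prior use of Nucala for asthma" as a subgroup, and prior use of other biologics as another.

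SAP 6.2.2 words the anchor without the indication: "Retrospective period is defined as time (within 12 weeks) before the first dose of Nucala". SAP 4.6.4 contains neither prior-use subgroup. SAP 4.8 states: "There were no changes or deviations to the originally planned statistical analysis".

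**The concern.** The anchor and the label describe different things. The anchor is the start of Nucala for one indication; the label refers to time before any Nucala. They coincide only for participants who never had Nucala for asthma. For someone already on it, part or all of the 12- or 48-week window is time on the drug.

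At stake is the study's own before/after reading: hospitalization, emergency-visit and asthma-exacerbation rates, organ-system symptoms, and the change in oral corticosteroid (OCS) dose from the retrospective period. If the reference mixes exposed and unexposed participants in unknown proportion, the change cannot be read as the Protocol describes it. The two Protocol subgroups that mark these participants are also missing from the SAP, with no declared change.

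**Working it through.** The plan gives no figure for this point, so the first part compares texts and the second is an illustration on assumed inputs.

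**Comparison of the documents**

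1. *Can prior users enter?* Protocol 3.3 has no criterion against prior Nucala for asthma or a prior biologic. The only exclusion tied to Nucala use concerns an interruption of treatment for EGPA of more than 12 weeks.
2. *Are they separated in the retrospective results?* The hospitalization and emergency-visit models (SAP 4.3.1.2.3 and 4.3.1.2.4) have no covariate and are fitted to the retrospective period as a whole. Symptoms (4.3.1.2.1) and OCS percent change (4.3.1.2.5) are summarized over the Treated Population (TP). None of these distinguishes prior users.
3. *Are they visible elsewhere?* SAP 6.1.4 summarizes retrospective medication by ingredient and lists it, so use within the 12-week window may be seen. It shows no outcome by prior use and does not name Nucala for asthma.
4. *Is the anchor consistent?* SAP 4.1.2 (in words) and 4.5.1 specify the EGPA indication; SAP 6.2.2 and the bracketed formulas in 4.1.2 do not. For a prior asthma user, 6.2.2 read literally moves the window before the first asthma dose, wholly or partly outside the period for which data are collected.
5. *Do the windows match?* Events are counted over 336 days and medication over 84. Use that ended in the other 336 − 84 = 252 days (Weeks −48 to −12) falls outside the medication window but could affect the event counts.
6. *Subgroups.* Protocol 4.7 lists 16 and SAP 4.6.4 lists six. Neither prior-use subgroup is among the six.

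**Illustration (both inputs assumed)**

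Let f be the share of participants with prior treatment in the window, and r their event rate relative to unexposed participants. The retrospective offset is 48/52 year for everyone, so the intercept-only model returns the participant-weighted mean rate. Relative to the unexposed rate:

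pooled reference = (1 − f) + f × r

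If the true ratio of observation-period rate to unexposed rate were 0.50 (also assumed), the ratio a reader would form is 0.50 / pooled reference. For f = 0.30 and r = 0.5: 0.70 + 0.15 = 0.85, and 0.50 / 0.85 = 0.588.

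Each cell gives the pooled reference, then the apparent ratio:

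| f | r = 0.3 | r = 0.5 | r = 0.8 | r = 1.3 |
|---|---|---|---|---|
| 5% | 0.965; 0.518 | 0.975; 0.513 | 0.99; 0.505 | 1.015; 0.493 |
| 10% | 0.93; 0.538 | 0.95; 0.526 | 0.98; 0.510 | 1.03; 0.485 |
| 30% | 0.79; 0.633 | 0.85; 0.588 | 0.94; 0.532 | 1.09; 0.459 |
| 50% | 0.65; 0.769 | 0.75; 0.667 | 0.90; 0.556 | 1.15; 0.435 |

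With r below 1 the improvement is understated. With r above 1, as when prior users were sicker, it is overstated.

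**The case against.** The other side has a fair case.

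- *Status before the EGPA regimen is a legitimate reference.* The indication is for patients who respond inadequately to existing therapies, so background treatment is expected, and the Protocol collects these data only for reference. This stands for other biologics: time on them is truly before Nucala, and the residual issue is confounding. It does not rescue the label for participants on Nucala for asthma.
- *The wording in SAP 6.2.2 is shorthand.* Probably so, since 4.1.2 uses the same short form in its own formulas and 4.5.1 names the indication. It still leaves two readings for exactly the participants in question.
- *The missing subgroups are not targeted.* Most of the 16 are absent, Protocol 4.7 defers details to the analysis plan, and SAP 4.6.4 leaves room for later additions. That makes it a general undeclared reduction; the statement in SAP 4.8 is still inaccurate.
- *The stakes are low.* The study is descriptive, the two periods' rates are estimated independently with no ratio planned, and Protocol 5 already advises caution on effectiveness. This stands and limits the weight of the point.

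A reader might infer that restoring the two subgroups would expose the problem. It would not do so alone: the outputs in SAP 4.6.4 are by observation or total period and do not include hospitalization, emergency visits or asthma exacerbation. The exploratory section of the SAP is redacted, so a relevant display there cannot be ruled out.

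**Conclusion.** The point holds in a limited form. The reference runs up to the first dose for EGPA, is described as preceding Nucala, and pools participants who may already have been on Nucala for asthma. SAP 6.2.2 and 4.1.2 need one wording, and SAP 4.8 does not match the subgroup list.

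Two stronger readings are not supported. A reader might infer that prior users are classified as untreated; neither document says so. A reader might also infer that the reference is known to be diluted by drug effect. The documents give neither f nor r, so neither size nor direction is established. Over f of 5% to 50%, the pooled reference is 1% to 35% below the unexposed rate for r of 0.3 to 0.8, and 1.5% to 15% above it for r = 1.3. These ranges rest wholly on assumption.

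Only descriptive secondary and exploratory before/after comparisons are touched. The primary adverse-event summaries do not use the retrospective reference, and the sample size of about 120 rests on adverse-event frequency alone. This is a worthwhile, inexpensive improvement, not a threat to the study's main aim.

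**What to change.** 1. In SAP 6.2.2 and the formulas in SAP 4.1.2, add *for EGPA* to the anchor.
2. Report how many TP participants had Nucala for asthma, and how many another biologic, recorded in the 12-week retrospective medication window.
3. Present the retrospective hospitalization, emergency or unscheduled visit and asthma-exacerbation rates, the retrospective symptoms, and the OCS change from the retrospective period for all TP, and again excluding participants with prior Nucala for asthma. Do the same separately for prior other biologics. Reserve the pre-Nucala label for the display without prior Nucala, and footnote that use stopped between Weeks −48 and −12 is not captured.
4. Restore the two Protocol 4.7 subgroups in SAP 4.6.4, or declare their removal in SAP 4.8.

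The cost is SAP wording and additional strata on existing tables, from data the schedule already collects. The downside is fewer participants in the restricted displays. Extending retrospective medication collection to 48 weeks is not proposed: it would change the Protocol's data collection and need ethics committee approval, and SAP 1.2 already describes the interim database lock as declared.

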4.2. Primary Endpoint(s) Analyses

4.2.1. Definition of endpoint(s)

The primary endpoints are as follows:

- Frequency of adverse events (AEs) / serious adverse events (SAEs)
- Frequency of AEs related to Nucala (adverse drug reactions, ADRs)
- Frequency of AEs of special interests (AESI)

4.2.2. Main analytical approach

The primary analyses will be based on the TP. Adverse events (AEs) will be coded using the Medical Dictionary for Regulatory Activities (MedDRA), with the maximum intensity of each AE determined by the investigator (as mild, moderate, severe or unknown).

All AEs, ADRs, SAEs, AEs leading to withdrawal from study, and AESIs will be summarized by the observation period and the total period (the observation period and the follow-up period), respectively. A separate summary of AEs by maximum intensity will be produced by the observation period and the total period, respectively.

The frequency and percentage of all AEs will be summarized and displayed in two ways: 1) in descending order by PT only and 2) in descending order by SOC and PT.

Separate summaries will be provided for ADRs. An ADR is defined as an AE for which the investigator classifies the possible relationship to study intervention as "Yes". A worst-case scenario approach will be taken to handle missing relatedness data, i.e. the summary table will include events with the relationship to study intervention as 'Yes' or missing. The summary table will be displayed by SOC and PT. The relationship of primary SOCs, Preferred Terms, and verbatim texts will be listed.

The number and percentage of participants who experienced the serious adverse event will be summarized.

The following will be considered adverse events of special interest (AESI) for the purpose of analyses: Hypersensitivity (including anaphylaxis), infections and malignant tumors, defined as safety specifications in the Japanese RMP.

AESI	Definition	Dictionary code
Hypersensitivity (including anaphylaxis)	Anaphylaxis reaction (SMQ/narrow)	20000021 (narrow)
	Excluding "10078117: Eosinophilic granulomatosis with polyangiitis" from PT contained in Hypersensitivity (SMQ/narrow)	20000214 (narrow)
Infections	Infections: Infections and infestations(MedDRA/J SOC)	MedDRA/J SOC: 10021881
Malignant tumors	Malignant tumors (SMQ/narrow)	20000227 (narrow) 20000228 (narrow)
	Lymphoma malignum (SMQ/narrow)	20000215 (narrow)

The summary be provided for AESI. The percentage will be calculated in two ways; one with number of participants with event as the denominator and the other with total number of participants as the denominator. The worst-case approach will be applied at participant level for the maximum intensity (i.e. a participant will only be counted once as the worst case from all the events experienced by the participant). For action taken to an event, a participant will be counted once under each action (e.g. if a participant has an event leading to both study discontinuation and dose reduction, the participants will be counted once under once under both actions).

Listings of all AEs and of subject numbers for individual AEs will be displayed. Reasons for considering as a SAE, AEs leading to withdrawal from study and AESIs will also be listed. In addition, patient profiles will be provided of patients with deaths.

Exposure-adjusted AE rate (the number of events per 1000 participant-years of exposure) for the AEs will also be summarized. This summary table will be produced by the

observation period and the total period (the observation period and the follow-up period), respectively.

The number of events per 1000 participant-years of exposure will be calculated as:

 $(1000 \times \text{number of AEs during the period}) / (total duration of exposure in days / 365.25)$

The derivation of the total duration of exposure in days is defined in 6.2.3.

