## 3.3. Eligibility Criteria

#### 3.3.1. Inclusion Criteria

Participants are eligible to be included in the study only if **all** of the following criteria apply:

- 1. Adult patients with EGPA of ≥20 years of age inclusive, at the time of signing the informed consent.
- 2. Participants must have a current clinical diagnosis of EGPA by physician.
- 3. Participants have continuously used Nucala for at least 96 weeks for the treatment of EGPA as mentioned in the current label in Japan.
  - Participants thus were registered and completed the Nucala PMS study (special drug use investigation; Protocol No. 208505, NCT03557060) prior to be enrolled in this study.
- 4. Physician's decision to continue treatment with Nucala for the treatment of EGPA as mentioned in the current label in Japan.
- 5. Prior to commencing any study related activities, participants must be able and willing to provide written informed consent.

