# 6.2.1. Time Period and Frequency for Collecting AE and SAE Information

All AEs should be monitored throughout the study. All AEs and SAEs must be recorded in the eCRF.

All AEs and SAEs will be collected from the signing of the informed consent form until the final study visit.

All SAEs will be recorded and reported to the sponsor or designee within 24 hours of recognition, as indicated in Section 9.3 (Appendix 3). The investigator will submit any updated SAE data to the sponsor within 24 hours of it being available. AEs related to Nucala will be recorded and reported to the sponsor or designee within 5 work days of recognition.

Investigators are not obligated to actively seek AE/SAEs after the conclusion of the study participation. However, if the investigator learns of any SAE, including a death, at any time after a participant has been discharged from the study, and they consider the event to be reasonably related to Nucala, the investigator must promptly notify the sponsor. As for death information, investigators are asked to report it to the sponsor throughout the study period regardless of whether the death is related to Nucala or not.

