6.2.6. Handling of Partial Dates

Element	Reporting Detail			
General	• Partial dates v displays.	will be displayed as captured in participant listing		
	• However, where necessary, display programs may impute dates as temporary variables for sorting data in listings only. In addition, partial dates may be imputed for 'slotting' data to study phases or for specific analysis purposes as outlined below.			
	• Imputed partial dates will not be used to derive study day, time to onset or duration (e.g., time to onset or duration of adverse events), or elapsed time variables (e.g., time since diagnosis). In addition, imputed dates are not used for deriving the last contact date in overall survival analysis dataset.			
Adverse Events	• Partial dates f following con	or AE recorded in the eCRF will be imputed using the ventions:		
	Study start date is defined as the date of dose of Nucala at Week 0.			
	Missing start day	If study start date is missing (i.e. participant did not start study), then set start date = 1st of month.		
		Else if study start date is not missing:		
		 If month and year of start date = month and year of study start date, then 		
		• If stop date contains a full date and stop date is earlier than study start		

Element	Reporting Detail		
		date, then set start date= 1st of month.	
		• Else set start date = study start date.	
		Else set start date = 1st of month.	
	Missing start day and month	If study start date is missing (i.e. participant did not start study), then set start date = January 1.	
		Else if study start date is not missing:	
		 If year of start date = year of study start date, then 	
		• If stop date contains a full date and stop date is earlier than study start date, then set start date = January 1.	
		• Else set start date = study start date.	
		Else set start date = January 1.	
	Missing end day	A '28/29/30/31' will be used for the day (dependent on the month and year).	
	Missing end day and month	No Imputation	
	Completely missing start/end date	No imputation	
Concomitant Medications/ Medical History	• Partial dates for will be impute	or any concomitant medications recorded in the CRF ed using the following convention:	
	Missing start day	If study start date is missing (i.e. participant did not start study), then set start date = 1st of month.	
		Else if study start date is not missing:	
		 If month and year of start date = month and year of study start date, then 	

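### Adverse events between consent and the Week 0 dose occur during long-term Nucala use but fall outside the period-based primary safety summaries

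*SAP*

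**What the plan says.** **Collection.** Protocol 6.2.1 states: "All AEs and SAEs will be collected from the signing of the informed consent form until the final study visit". The Schedule of Activities (Protocol 9.1) marks adverse events at Screening.

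**Periods.** SAP 6.2.2 separates the two periods: "Screening period is defined as 0-4 weeks before the date of dose of Nucala at Week 0", and "Observation period is defined as time from the date of dose of Nucala at Week 0". Screening can have no length at all, because Protocol 9.1 notes: "Screening and Week 0 can occur on the same day".

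**Tables.** SAP 4.2.2 sets the periods for AEs, adverse drug reactions (ADRs), serious AEs (SAEs) and AEs of special interest (AESIs): "All AEs, ADRs, SAEs, AEs leading to withdrawal from study, and AESIs will be summarized by the observation period and the total period". It defines the total period as observation plus follow-up, as Protocol 4.5 does. The exposure-adjusted rates in SAP 4.2.2 and the subgroup AE tables in SAP 4.6.4 use the same two periods.

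**Population.** Protocol 3.3.1 requires: "Participants have continuously used Nucala for at least 96 weeks for the treatment of EGPA". Safety analyses use the Treated Population, a subset of All Subjects Enrolled (SAP 3 and 4.1.1).

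**Participants who do not go on.** Protocol 3.1 classes as a Screen Failure someone who finishes the screening assessments but "does not continue in the study beyond Baseline or is subsequently found to be ineligible" before Baseline. SAP 6.1.1 is narrower. There, screening failure means not meeting the eligibility criteria, and early withdrawal means leaving during the observation period.

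**The concern.** Starting the AE tables at Week 0 is natural when Week 0 is the first dose. Here it is not: Week 0 is a routine dose in a course that has already run for at least 96 weeks. An AE between consent and that dose is an event during long-term Nucala use, collected under the protocol and, if serious, reportable within 24 hours. It belongs to the experience that the primary endpoint describes, yet neither named reporting period contains it.

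The sample size is justified by the chance of seeing at least one case of an uncommon AE. For such an event one case matters. A single malignancy, anaphylaxis or drug-related SAE in screening would be collected and assessed for causality, but would not be counted in the period-based tables.

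**Working it through.** **1. Where an event lands**

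| Start of AE | Observation-period table | Total-period table | Other output |
|---|---|---|---|
| Consent to day before Week 0 dose | No | No | AE listing; screen-failure reason if applicable |
| Week 0 dose to end of observation | Yes | Yes | AE listing |
| Follow-up (from first discontinuation + 29 days) | No | Yes | AE listing |

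The first row is collected under Protocol 6.2.1 but has no period-based count.

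**2. The plan's own figure**

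Inputs (Protocol 3.5, SAP 5): AE frequency p = 1.5%; probability P of at least one case = 70%, 80% or 90%; dropout 10%. Formula: n = ln(1 − P) / ln(1 − p), rounded up.

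- P = 80%: ln(0.20) / ln(0.985) = 106.5, so 107.
- P = 70%: ln(0.30) / ln(0.985) = 79.7, so 80.
- P = 90%: ln(0.10) / ln(0.985) = 152.4, so 153.
- Dropout: 107 / 0.90 = 118.9, so 119, stated as about 120.

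All are reproduced, and none is in dispute.

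**3. Time outside the tables**

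Inputs: N = 120; screening 0 to 28 days; 96 weeks = 672 days of follow-up, or 700 days with the 28 days that SAP 6.2.2 adds after stopping. Consent is assumed to fall inside the screening window, and all participants to be followed for the full 96 weeks.

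- Maximum screening time: 120 × 28 / 365.25 = 9.2 participant-years.
- Minimum: 0 (same-day screening).
- Time from Week 0: 120 × 672 / 365.25 = 220.8 participant-years, or 120 × 700 / 365.25 = 230.0.
- Largest share: 28 / (28 + 672) = 4.0%, or 28 / (28 + 700) = 3.8%.

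**4. Effect on seeing a rare event**

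The plan gives no time base for its 1.5%. Assume a constant hazard that yields 1.5% over 672 days, and the full 28 days of screening for everyone.

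- Chance of at least one such case during screening at N = 120: 1 − 0.985^(120 × 28/672) = 1 − 0.985^5 = 7.3%.
- Chance of at least one case from Week 0 only: 1 − 0.985^120 = 83.7%.
- Chance of at least one case with screening included: 1 − 0.985^(120 × 700/672) = 1 − 0.985^125 = 84.9%.
- At N = 107 the same calculation moves from 80.2% to 81.4%.

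The difference, about 1.2 percentage points, is the chance that such an AE is seen in screening and nowhere else. It is an upper limit, since shorter screening reduces it towards zero.

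**5. Analysis set**

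A participant who does not continue beyond Baseline is apparently outside All Subjects Enrolled, and so outside the Treated Population; the documents do not define the moment of enrolment. For that person the analysis set, as well as the period, can keep the event out of the tables. A participant who met the criteria but left before Week 0 fits neither the screening-failure nor the early-withdrawal definition in SAP 6.1.1.

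**The case against.** The case on the other side is substantial, and most of it limits the point.

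- **The events are not lost.** SAP 4.2.2 lists all AEs, the reasons for seriousness, AESIs and AEs leading to withdrawal, and gives profiles for deaths, with no period limit. SAP 6.1.1 summarizes screen-failure reasons. The pharmacovigilance plan (Protocol 9.6) puts a summary of product-related AEs in the final report, also without a period limit. A reader might infer that screening events reach no summary of any kind; these passages do not support that. What stands is that a listing or an uncoded disposition reason is not a count, and that the pharmacovigilance summary covers related events only and is not specified in the SAP.
- **An overall table may be intended.** Protocol 4.5 describes the period tables as additional, and two sentences in SAP 4.2.2 (AEs by preferred term and system organ class; participants with an SAE) name no period. It therefore goes too far to say that every safety table begins at Week 0. But nothing says that an overall table would begin at consent.
- **The window is stated and conventional.** Protocol 4.5 itself defines the total period, and the study is descriptive. This stands, and it is a reason to leave that period alone and add to it.
- **Selective loss is not shown.** A reader might infer that events which end participation are systematically removed. The documents do not establish this. Stopping Nucala does not in itself end participation, because such participants are followed up where possible. A physician's decision in screening not to continue Nucala fails inclusion criterion 4, and that reason is summarized. Someone who leaves before finishing screening may not be a Screen Failure under Protocol 3.1 at all.
- **Partial dates do not lower the counts.** SAP 6.2.6 says "Study start date is defined as the date of dose of Nucala at Week 0" and moves some AEs with a missing start day or month to that date. This can bring a screening event into the tables; it removes none. It is a minor inconsistency between full and partial dates and does not add to the concern.

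**Conclusion.** The point holds as a gap in reporting. AEs from consent to the Week 0 dose are collected in people already on long-term Nucala, but are absent from the period-based AE, ADR, SAE and AESI summaries and from the exposure-adjusted rates.

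The gap is at most about 4% of on-study time and may be zero. The chance of detecting a 1.5% event changes by no more than about 1.2 percentage points, under a constant hazard, 28 days of screening for all and complete follow-up. Overall rates and the sample-size rationale are essentially unaffected. The reason to act is that for a single rare serious, drug-related or special-interest event the omission from these tables is complete.

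**What to change.** 1. Keep the observation-period and total-period tables as defined. In SAP 4.2.2, add a separate consent-to-Week-0 column or table for AEs, SAEs, ADRs and AESIs. If a rate is shown there, use the days from consent to Week 0 as its own denominator.
2. Base it on all participants who signed consent, including those who did not complete screening or did not continue beyond Baseline, and say at what date their column ends. Do not use the Screened Population in SAP 3: it requires completed screening and would miss anyone who stopped during it.
3. Align the screening-failure definition in SAP 6.1.1 with Protocol 3.1, so that an eligible participant who stops before Week 0 is classified. The wording should also say how someone who leaves before finishing screening is classified.

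Moving the start of the total period to consent is not recommended. It would depart from Protocol 4.5, change the exposure calculation and require an entry in SAP 4.8.

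The cost is one small extra table or column and some SAP wording. Participants who continue need no new data, since Protocol 6.2.1 already requires these AEs in the eCRF. For screen failures, check the eCRF entry guideline cited in Protocol 3.1, which is not among the documents, to confirm what is recorded.
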